Ketamine is a well-known analgesic that has been frequently used pre-, intra-, and post-operatively. The analgesic property of ketamine is dose dependent, but it is generally believed to be short lived, as the medication is metabolized within an hour.⁷ Although ketamine has been shown in animal studies to block central sensitization to mediate long-acting analgesia,⁸ this remains to be proven in clinical practices.⁹ Low dose ketamine (<0.5mg/kg/hr) is used routinely and safely for inpatient pain management¹⁰ and outpatient management of certain chronic neuropathic pain conditions such as complex regional pain syndrome.¹¹

Meanwhile, in the last ten years or so, a number of studies have provided exciting evidence that ketamine has rapid-onset antidepressant effects that may last up to seven days.^{12-14,15,16} Several mechanisms have been proposed to explain this mood elevating effect of ketamine including increased glutamate transmission^{17,18} and increased brain derived neurotrophic factor expression.¹⁹ Animal studies have confirmed that ketamine, given as an analgesic, has rapid and

enduring mood elevating effects in postoperative pain states.²⁰ Despite its wide use in the postoperative setting as an analgesic, however, few clinical studies have examined the effect of ketamine on mood and functional status in the postoperative patients. Currently, there is only one study on peri-operative use of ketamine in bariatric patients,²¹ which showed that pre-inductive use of ketamine leads to early extubation and decreased total use of opioids. No study, in contrast, has examined the effects on mood and functional recovery with the use of ketamine postoperatively for pain control.

A number of pro- and anti-inflammatory cytokines (interleukin IL-1, IL-2, IL-6, IL-8, IL-10, IL-12, and tissue necrosis factor, TNF- α) have been linked with stress and mood regulation.²² Some of these cytokines, particularly IL-1, IL-6 and TNF- α , have also been implicated in pain states as well. In addition, reduced serum levels of brain derived neurotrophic factor (BDNF) have been described to correlate with pain as well as depressed mood, and ketamine has been hypothesized to increase BDNF levels.²³ However, there has been limited study in postoperative pain on the involvement of cytokines and neurotrophic factors as potential markers for assessing pain and predicting analgesia.

Study Rationale

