Ketamine, given for postoperative pain control, can be hypothesized to have long lasting analgesic effects as well as effects on improving mood and function in the postoperative period. Ketamine can be administered as a single dose in the post-anesthetic care unit (PACU), where patients are closely monitored for potential side effects. We hypothesize that postoperative use of ketamine should lead to improvement in pain indices including visual analog scale (VAS), a decrease in opioid requirement, mood improvements as measured by psychometric indices, and finally improvements in functional measures including early mobility and faster discharge from the hospital. In addition, we will assess serum levels of IL-1, 6, TNF- α , and BDNF to see if alterations in levels of cytokines and neurotrophic factors occur with postoperative pain and how ketamine treatment may influence the levels of these biomarkers.

Study Objective

Specific aim 1: examine the effect of a single, subanesthetic dose (0.4mg/kg) of ketamine vs. saline control on mood and postoperative function in patients who have undergone gastric bypass and sleeve gastrectomies.

Pain relief and changes in postoperative mood and function will be assessed using both patient report, in the forms of a series of questionnaires, and medical chart review. The questionnaires we use will be Beck Depression Inventory (BDI), Visual Analog Scale (VAS), McGill's short form, QoR-15 form and the Montgomery-Asberg Depression Rating Scale (MADRS). Please see below for a detailed discussion of these forms. In addition, from the chart review we will monitor length of stay during hospitalization, opioid usage per hour during the PACU stay before and after ketamine infusion, total opioid usage per day throughout the hospital stay, time to out of bed to chair, and spirometry use after ketamine infusion.

Specific aim 2: examine the effect of a single, subanesthetic dose (0.4mg/kg) of ketamine vs. saline control on inflammatory cytokines and neurotrophic factors in the postoperative period.

We will examine the effect of ketamine on proinflammatory markers and neurotrophic factors known to be linked with pain. We will examine levels of interleukin factor 1 and 6 (IL-1, IL-6), TNF- α , and BDNF. This aim will provide potential mechanism of action for ketamine.

Overall study design and plan

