An additional component of the study, which is entirely optional, is to obtain patient serum samples (about two teaspoons) in the operating room and 15 minutes and 4 hours after ketamine infusion. We will use these samples to assess levels of IL-1, IL-6, TNF- α , and BDNF, which are markers for pain. In addition, with patient consent, we will also store serum samples for future research use to measure other cytokines and neurotrophic factors and molecular markers associated with pain and depression.

Study site: Tisch Hospital

Outcome measures

Primary outcome measure: scores on the following questionnaires: 1) The Beck Depression Inventory (BDI); 2) Visual Analog Scale (VAS) score; 3) McGill's short form; 4) QoR-15 form; and 5) Montgomery-Asberg Depression Rating Scale (MADRS). The BDI and MADRS provide assessments for mood and function, VAS and McGill's assess pain, and QoR-15 assesses patient's overall satisfaction with postoperative recovery.

After consent is achieved in the pre-admission clinic prior to surgery, patients will be asked to fill out BDI, MADRS and QoR-15 forms to establish baseline scores. The BDI, MADRS will be filled out on postoperative days (POD) 0 after the infusion of ketamine, and BDI, MADRS and QoR-15 forms will be repeated on POD1, 2 and 7. McGill's short form will be filled out prior to discharge from the PACU and on POD 1, 2 and 7. VAS will be filled prior to PACU discharge, and every day while patient is in the hospital and on POD 7. VAS is a routine part of hospital care and will be administered daily whether a patient is enrolled in the study or not. If a patient has been discharged prior to POD2 or 7 (patients typically are discharged on POD2 or 3 in our practice), then a member of the study team will contact the patient by telephone to fill out these questionnaires.

Secondary outcome measures: 1) length of stay during hospitalization; 2) opioid usage per hour during the PACU stay before and after ketamine infusion; 3) opioid usage per day throughout the hospital stay; 4) time to out of bed to chair (OOB); 5) spirometry use 4 hours after the termination of ketamine infusion; 5) anti-emetic use in the PACU.

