Sample Size Justification: Previous studies on the antidepressant effects of ketamine on depressed patients typically yield a mean difference in psychometric measures of 40%, with a standard deviation of roughly 40% as well. Power analysis yields $n = 50$ patients in each arm. This will allow for us to detect a true difference in the mean value of our outcome variable of $\pm 22.5\%$ with a probability (power) of 0.8. The type I error probability associated with this test of the null hypothesis that the population means of the ketamine versus control groups are equal is 0.05.

Statistical Analysis: For this study, descriptive statistics will be performed for all data and subgroups as needed:

- 1) Outcome tests (see above), N (%) for each category, showing absolute values, absolute

and percent differences, stratified by treatment etc.

- 2) Demographics showing continuous parameters (age, height, weight, etc.) as mean + SD; categorical parameters, as N (%); all also stratified by treatment.

Analysis of variance (ANOVA) test with repeated measures will be performed to determine within-patient effects (time) and between patient effects (treatment) on outcome measures. Pearson correlation will be used to assess relationships between continuous variables, and Spearman's Rho will be used for ranked data. For non-normally distributed, the Kruskal-Wallis test will be used for global significance, and Mann Whitney for subsequent pairwise comparisons.

Exploratory analysis will fit continuous (VAS score, length of stay in the hospital) and categorical (ordinal outcome data) to a Logistic Regression model which predicts the treatment bivariate (IV ketamine or placebo).

Interim Data analysis: An interim data analysis will be performed after a total of 50 patients have completed the study. An analysis of primary and secondary endpoints will be analyzed, and if the primary endpoints are met, we will opt to terminate the study.

DATA SAFETY AND MONITORING PLAN

Timeline

- 1) Estimated start date: Sept 1, 2013
- 2) Estimated time for start-up: 2 months
- 3) Time allotted for enrollment: 2 years
- 4) Estimated study end date: August 30, 2015

Data acquisition and management

The research material obtained from human subjects in this proposed study will be collected solely for research purposes. It will be as follows:

- a. *Clinical information* obtained by medical history, questionnaires and interviews.

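### The planned Pearson and Spearman correlations do not say how treatment arm is handled; a simple coefficient across both arms on post-infusion data could show a marker–pain link created only by ketamine acting on both variables.

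*Combined protocol and SAP*

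**What the plan says.** The Statistical Analysis section, and its repeat under the Data Safety and Monitoring Plan, covers correlations in one sentence: "Pearson correlation will be used to assess relationships between continuous variables, and Spearman's Rho will be used for ranked data". It gives no variables, time points or analysis set, and does not mention arm.

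The same section does bring treatment in elsewhere:
- Descriptive outcome summaries give absolute values and absolute "and percent differences, stratified by treatment etc".
- The repeated-measures ANOVA examines "within-patient effects (time) and between patient effects (treatment) on outcome measures".
- The exploratory logistic regression has treatment as its dependent variable.

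On the biology:
- Study Rationale, on pain and mood: "Ketamine, given for postoperative pain control, can be hypothesized to have long lasting analgesic effects as well as effects on improving mood".
- Background, on one marker: "ketamine has been hypothesized to increase BDNF levels".
- Study Rationale, on all four markers, asks "how ketamine treatment may influence the levels of these biomarkers" without giving a direction.

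On the purpose of the markers, the Background speaks of "potential markers for assessing pain and predicting analgesia", and the study design section says "We will use these samples to assess levels of IL-1, IL-6, TNF- α , and BDNF, which are markers for pain". Serum is taken at baseline and at 15 minutes and 4 hours after the infusion. The serum component is optional, and Outcome measures classes the markers as exploratory.

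**The concern.** A correlation across two randomised arms mixes the association among patients given the same treatment with the association produced because both variables have different means in the two arms. If ketamine raises BDNF and lowers pain by unrelated routes, ketamine patients sit at high BDNF and low pain and placebo patients at the opposite corner. The coefficient is then negative with no link inside either arm.

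The direction matters here. The Background reports that low BDNF goes with more pain and worse mood, which is also a negative correlation. The artefact would therefore look like confirmation of the protocol's premise.

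At stake is the reading of the marker data. An unadjusted coefficient cannot separate a drug that affects both variables from a marker that tracks pain, and it misleads most when the drug works.

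**Working it through.** **Inputs from the documents.** 100 patients, 1:1 (study design section). Sample Size Justification gives a 40% effect and a 40% SD from earlier antidepressant studies, a detectable difference of 22.5%, power 0.8 and alpha 0.05.

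**The plan's own figure.** n per arm = 2 × (1.960 + 0.842)² × (40/22.5)² = 49.6, rounded up to 50. Power at 50 per arm is Φ(0.5625/√(2/50) − 1.960) = Φ(0.853) = 0.803. The stated 50 reproduces, with a two-sided test inferred from the ± sign. It concerns the comparison of means; the documents state no figure for the correlations.

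**Assumptions.** The documents give no biomarker effect or SD, and no number for the serum sub-study. I borrow the protocol's two standardised effects as a range: 22.5/40 = 0.5625 and 40/40 = 1.0, with 0.8 between them. I take n = 100 (everyone gives serum) and n = 50 (an assumed half).

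**Induced correlation.** Let ketamine shift the marker by d1 and the outcome by d2, in within-arm SDs, with zero within-arm correlation and equal arms. The between-arm covariance is d1·d2/4 and each total variance is 1 + d²/4, so

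r = (d1·d2/4) / √[(1 + d1²/4)(1 + d2²/4)].

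- d1 = d2 = 0.5625: 0.0791/1.0791 = 0.073
- d1 = d2 = 0.8: 0.16/1.16 = 0.138
- d1 = 0.5625, d2 = 1.0: 0.1406/√(1.0791 × 1.25) = 0.121
- d1 = d2 = 1.0: 0.25/1.25 = 0.200
- d1 = 0, d2 = 1.0: 0

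The sign follows the directions of the two shifts; the size does not depend on it.

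**Chance of a significant result at nominal two-sided 5%.** By Fisher's z, this is approximately Φ(atanh(r)·√(n − 3) − 1.96) plus the small opposite tail. For d1 = d2 = 1.0 and n = 100: 0.2027 × √97 = 1.997, and Φ(0.037) = 51%. Simulation of the unadjusted Pearson test (40,000 trials per case) is shown beside it.

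| d1, d2 | \|r\| | n = 100: Fisher z / simulated | n = 50: Fisher z / simulated |
|---|---|---|---|
| 0, 1.0 | 0 | 5% / 4.8% | 5% / 5.0% |
| 0.5625, 0.5625 | 0.07 | 11% / 11.0% | 8% / 8.2% |
| 0.5625, 1.0 | 0.12 | 22% / 22.5% | 13% / 13.3% |
| 0.8, 0.8 | 0.14 | 28% / – | 16% / – |
| 1.0, 1.0 | 0.20 | 51% / 53.1% | 28% / 29.4% |

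Unadjusted Spearman (10,000 trials per case) is nearly the same: 10.8% and 53.0% at n = 100 for the smallest and largest equal shifts.

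**After adjustment for arm.** The partial Pearson correlation (each variable centred within arm, n − 3 degrees of freedom) has mean r of about 0 and rejects in 4.8% to 5.3% of trials in every simulated case.

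**The case against.** The strongest reply is that the plan never commits to the analysis being criticised. A reader might infer from the missing arm term that the coefficients will be run over all patients. The documents do not say so; they are silent on pooling, stratification and time point. The marker-versus-pain pairing is likewise inferred from the markers' stated purpose. This stands: the supportable statement is that pairs, times and arm are unspecified, and that the simplest execution of the sentence would be unadjusted.

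Four more limits stand:
- It would be wrong to infer that treatment is recognised only in the descriptive tables. The ANOVA and the logistic regression both use it.
- It is tempting to say that ketamine is hypothesised to move all the markers. A direction is given only for BDNF; for IL-1, IL-6 and TNF-α the effect is an open question.
- The 40% and 22.5% figures belong to psychometric measures and the trial's outcome variable, so the sizes above are a range under assumption, not an expected biomarker effect. Correlating a baseline marker with later pain, as one might do to predict analgesia, is the d1 = 0 case and is not inflated.
- Aim 2 is framed as a randomised comparison of marker levels between ketamine and saline. That comparison does not depend on the correlations.

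None of this removes the point. The Study Rationale also asks whether marker levels change with postoperative pain, and the only correlation method offered gives no protection against the shared drug effect. Adjustment for arm would not by itself prove a biological link: other analgesics are unrestricted and could move both variables. It removes only the part that is due to randomised treatment.

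**Conclusion.** The point holds as a gap in specification, and closing it is a free improvement. If post-infusion markers are correlated with pain or mood by a simple coefficient across both arms, and ketamine shifts both, the coefficient is biased away from zero with no within-arm link. With equal shifts of 0.56 to 1.0 SD, the false-positive rate rises from 5% to about 11% at the low end. At the high end it reaches about 52% with 100 patients (51% by approximation, 53% by simulation) and up to 29% with 50. The shifts on the biomarkers and the 50 are assumptions.

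A reader might go further and conclude that Aim 2 fails or that the trial's main result is at risk. The documents do not support that: the serum component is optional and exploratory, and neither the primary comparison nor the sample size is touched.

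**What to change.** Replace the correlation sentence, in both copies of the Statistical Analysis section, with text such as:

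> Correlations between post-infusion variables, including changes from baseline, will be partial correlations adjusted for treatment arm (partial Pearson for continuous data, partial Spearman for ranked data), using one value per patient at a named time point. The variable pairs and time points are: [list]. The coefficient within each arm will be shown descriptively.

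The list of pairs is for the investigators to complete before unblinding. Any unadjusted coefficient across both arms should be labelled descriptive.

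The cost is this short replacement text, the list of pairs, and one degree of freedom per correlation. No extra patients, samples or procedures are needed.

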Randomized, double-blind, placebo controlled study on the effect of a single postoperative administration of low dose ketamine after gastric bypass and gastrectomy surgeries

Primary Investigator: [name]. Ph.D.

New York University Langone Medical Center, Department of Anesthesiology

Study Number: S13-00719

Background

Bariatric surgeries for the treatment of obesity and type II diabetes represent one of the most common abdominal operations, with over 300,000 cases performed in 2011.¹ Postoperative care is a critical component for outcome from these procedures. Optimal postoperative pain management, however, can be difficult to achieve. While many incisions are small, a significant proportion of patients who undergo bypass or sleeve gastrectomy still stay in the hospital for more than two to three days, and patients can suffer from a combination of incisional and visceral pain. Pain control currently is achieved through a combination of opioids, Acetaminophen, and NSAIDs. Opioids are the most powerful analgesic in this group. Opioids, however, are well known to cause sedation and respiratory depression, which can significantly impact respiratory status of bariatric patients, many of whom already suffer from respiratory compromise due to obesity and obstructive sleep apnea. NSAIDs, meanwhile, may increase the rate of bleeding complications. Thus, additional analgesics are needed to achieve optimal pain control.

A key component of postoperative pain experience is depressed mood, which further complicates functional recovery.^{2,3} Bariatric patients, in particular, have a high co-morbidity of depression, which can be worsened by postoperative pain.⁴⁻⁶ Optimal pain control, on the other hand, has been shown to improve patient satisfaction, elevate mood, and allow early participation in physical rehabilitation such as early mobility, all of which contribute to better surgical outcome. Studies are needed, however, to examine additional postoperative measures that can enhance functional recovery in bariatric patients.

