Sample Size Justification: Previous studies on the antidepressant effects of ketamine on depressed patients typically yield a mean difference in psychometric measures of 40%, with a standard deviation of roughly 40% as well. Power analysis yields $n = 50$ patients in each arm. This will allow for us to detect a true difference in the mean value of our outcome variable of $\pm 22.5\%$ with a probability (power) of 0.8. The type I error probability associated with this test of the null hypothesis that the population means of the ketamine versus control groups are equal is 0.05.

Statistical Analysis

For this study, descriptive statistics will be performed for all data and subgroups as needed:

- 1) Outcome tests (see above), N (%) for each category, showing absolute values, absolute and percent differences, stratified by treatment etc.
- 2) Demographics showing continuous parameters (age, height, weight, etc.) as mean + SD; categorical parameters, as N (%); all also stratified by treatment.

Analysis of variance (ANOVA) test with repeated measures will be performed to determine within-patient effects (time) and between patient effects (treatment) on outcome measures. Pearson correlation will be used to assess relationships between continuous variables, and Spearman's Rho will be used for ranked data. For non-normally distributed data, the Kruskal-Wallis test will be used for global significance and Mann Whitney for subsequent pairwise comparisons.

Exploratory analysis will fit continuous (VAS score, length of stay in the hospital) and categorical (ordinal outcome data) to a Logistic Regression model which predicts the treatment bivariate (IV ketamine or placebo).

Interim Data analysis

An interim data analysis will be performed after a total of 50 patients have completed the study.

An analysis of primary and secondary endpoints will be analyzed, and if the primary endpoints are met, we will opt to terminate the study.

Data Safety and Monitoring Board (DSMB)

In addition to the PI, [name], an independent patient safety DSMB panel will also review study documents and safety data on a routine basis. This board will meet once every three months, and more frequently as needed. In addition, the board will meet with study coordinator and assistant after a total of 50 patients have completed the study to perform an interim analysis. This board will include the additional following members from the department of anesthesiology.

1. [name]
2. [name]

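### The exploratory logistic regression predicts treatment from the outcomes; if the outcomes enter together, its coefficients are not ketamine's effects on them (low priority)

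*Combined protocol and SAP*

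**What the plan says.** The combined protocol and SAP describes the exploratory analysis in the Statistical Analysis section and repeats it unchanged under the Data Safety and Monitoring Plan. It will "fit continuous (VAS score, length of stay in the hospital) and categorical (ordinal outcome data) to a Logistic Regression model", and that model is specified as a "Logistic Regression model which predicts the treatment bivariate (IV ketamine or placebo". Treatment, assigned 1:1 by a randomisation list, is therefore the dependent variable. The predictors follow treatment: length of stay is known only at discharge, and the VAS schedule under Outcome measures starts in the PACU, with no preoperative score listed.

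The plan does not say whether the outcomes enter one at a time or together, which VAS time point is used, or how the coefficients will be read. One sentence lists several outcomes and a single model, so joint entry is a natural reading, but single entry is not excluded.

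Aim 1, under Study Objective, is to "examine the effect of a single, subanesthetic dose (0.4mg/kg) of ketamine vs. saline control on mood and postoperative function". Other parts of the Statistical Analysis section do run in that direction. The repeated-measures ANOVA tests "between patient effects (treatment) on outcome measures", rank tests are named for non-normal data, and the descriptive tables are planned as "showing absolute values, absolute and percent differences, stratified by treatment".

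**The concern.** A model that explains assignment by outcomes does not answer how much ketamine changes an outcome. With several outcomes in the model, each coefficient asks whether that outcome helps to tell the arms apart once the others are known. When outcomes are correlated, that differs from the treatment effect: an unaffected outcome can be flagged, an affected one missed, and one that improves less than another can take the wrong sign.

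Correlation is plausible here. The Background states "A key component of postoperative pain experience is depressed mood, which further complicates functional recovery", although no coefficient is given. The Study Rationale expects benefit on VAS together with "improvements in functional measures including early mobility and faster discharge from the hospital", so joint benefit is the case that the trial hopes for. At stake is how a reader interprets the exploratory per-outcome results, in particular for length of stay, a listed secondary outcome.

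**Working it through.** **Inputs from the documents.** 50 per arm, SD 40%, detectable difference 22.5%, power 0.8 and type I error 0.05 (Sample Size Justification). The error is taken as two-sided because the difference carries a plus/minus sign.

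**Assumptions.** Two outcomes, labelled VAS and stay; normal, with equal covariance in both arms; within-arm correlation ρ of 0, 0.3, 0.5 or 0.7; a negative shift is an improvement. The 0.5625 SD shift is the plan's psychometric figure, borrowed for VAS and stay. The 0.3 SD shift is assumed.

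**The plan's own figure.** n per arm = 2 × (1.96 + 0.8416)² × (40/22.5)² = 2 × 7.849 × 3.1605 = 49.6, so 50. Power at 50 is 0.803 (0.795 by t-test). The figure reproduces, and 22.5/40 = 0.5625 SD.

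**Coefficients under joint entry.** The log-odds of treatment given the outcomes have slopes equal to the inverse covariance matrix times the vector of mean differences d. For two standardised outcomes:

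b(stay) = (d_stay − ρ·d_VAS)/(1 − ρ²), and likewise for VAS.

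For example, with ρ = 0.5, d_VAS = −0.5625 and d_stay = 0: b(stay) = 0.28125/0.75 = +0.375 and b(VAS) = −0.5625/0.75 = −0.75.

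| ρ | VAS −0.5625, stay 0: b(VAS), b(stay) | VAS −0.5625, stay −0.3: b(stay) | Both −0.5625: each b |
|---|---|---|---|
| 0 | −0.56, 0 | −0.30 | −0.56 |
| 0.3 | −0.62, +0.19 | −0.14 | −0.43 |
| 0.5 | −0.75, +0.38 | −0.03 | −0.38 |
| 0.7 | −1.10, +0.77 | +0.18 | −0.33 |

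In the middle setting the sign reverses once ρ exceeds 0.3/0.5625 = 0.53. Only at ρ = 0 do the coefficients equal the effects in SD units.

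**Rates at 50 per arm under joint entry** (3,000 to 4,000 simulated trials per setting, Wald tests at two-sided 0.05, Monte Carlo error below 1 point):

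| Result, % of trials | ρ = 0 | 0.3 | 0.5 | 0.7 | Direct comparison |
|---|---|---|---|---|---|
| VAS −0.5625, stay 0: stay significant | 5 | 13 | 33 | 73 | about 5 |
| VAS −0.3, stay 0: stay significant | 5 | 7 | 13 | 28 | about 5 |
| Both −0.5625: power per outcome | 75 | 49 | 33 | 20 | about 80 |
| VAS −0.5625, stay −0.3: stay coefficient has wrong sign | 8 | 25 | 46 | 74 | 7 |
| Same setting: wrong sign and significant | 0 | 0.4 | 1.5 | 9 | not computed |

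The 7% is Φ(−0.3/√(2/50)) = Φ(−1.5) = 0.067.

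**What stays sound under joint entry.** With neither outcome shifted, each is flagged in 4–5% of trials. The overall test, which asks whether the outcome profile differs by arm, rejects in about 5% under the null. It has power of 95%, 89%, 83% and 79% across the four correlations when both outcomes improve by 0.5625 SD.

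**Single entry.** False flags are 4–5% and power is 78–80%, the same as the t-test. For an outcome entered as categories, the odds ratios are identical whichever variable is the response. For VAS and stay, the coefficient is a log-odds of assignment per unit of outcome, not points or days.

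**The case against.** The strongest reply is that no error follows from the text as written. Joint entry is not stated, and under single entry the test is as good as a t-test. Nothing says that the coefficients will be presented as treatment effects: a model that predicts the arm from outcomes is a recognisable discriminant analysis with a valid overall test. Treatment effects are left to the ANOVA, the rank tests and the descriptive differences, which a reader would see beside any odd coefficient. All of this stands, and it limits the weight of the point. It does not remove it, because the plan leaves the analyst free to enter outcomes jointly and gives no warning about reading the coefficients.

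The magnitudes are also open to challenge. The high false-flag rates need a strong correlation and a large VAS shift. Stay is coarse ("patients typically are discharged on POD2 or 3 in our practice"). With stay cut into four assumed whole-day categories, the false-flag rates become 5%, 12%, 28% and 62%. The two-outcome simulation stands in for a model that the plan does not fully specify. These points stand too.

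A reader might infer from the wrong-sign rates of up to 74% that the trial would often conclude that ketamine prolongs stay. The figures do not support that: those are point estimates regardless of significance, and a significant wrong-signed coefficient occurs in at most about 9% of trials.

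**Conclusion.** The point holds as a low-priority correction. The exploratory model is written in the reverse direction to aim 1 in both places, and nothing elsewhere corrects it. If outcomes enter jointly and are correlated, the per-outcome coefficients are not ketamine's effects: false flags for an unaffected outcome run from about 5% to 73%, and power per outcome falls from about 75% to 20%, over correlations from 0 to 0.7 with a 0.5625 SD shift. Those sizes rest on assumed correlations, assumed effects and a two-outcome normal model.

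A reader might go further and infer that the trial's treatment comparison is itself reversed or invalid. The documents do not support that. The model is labelled exploratory, the sample size does not use it, and the interim rule refers to the primary endpoints without invoking it. The ANOVA, rank tests and descriptive differences compare the arms in the right direction. Nor is the logistic test invalid as such: the single-entry tests and the joint overall test are both sound.

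**What to change.** Replace the sentence in both places with, for example: *For each exploratory outcome, a regression model suited to its type will be fitted with the outcome as response and randomised treatment as explanatory variable; the treatment effect will be reported with a 95% confidence interval.* The choice of model family can be left to the trial statistician.

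If the sponsor wants the joint question, keep the present model but label it a discriminant analysis, state that outcomes enter together, report only its overall test, and say that its coefficients are not treatment effects.

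The cost is one sentence in two places and minor programming; no new data, visits or patients are needed, and 50 per arm is unchanged. The downside is that the per-outcome models partly repeat the group comparisons already planned.
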